The purpose is to investigate the relationship between high total intake of systemic steroids in patients with upper and lower airway disease, low endogenous cortisol production, and reduced bone density and structure. Additionally, through an exploratory follow-up (pilot project) study, to investigate whether improved adherence to local steroid treatment and biologic medication would decrease the patient's endogenous cortisol production.

Hypothesis/research question:

Patients with CRS/CRSnNP/CRSwNP who have received systemic steroids have an impact on the adrenals with low basal P-cortisol (below 500nmol), abnormal response to stimulation with ACTH (synacthen test) measured at the final P-cortisol. Additionally, a reduced increase (delta value) in P-cortisol is expected in connection with a synacthen test. These patients also have an affected bone density and structure with a higher incidence of osteopenia and osteoporosis than expected for this age group. Patients with CRS/CRSnNP/CRSwNP who can improve their adherence to >80% have an increasing impact on P-cortisol.

Primary outcome:

The primary outcome is to investigate whether newly referred patients with upper and possible lower respiratory tract diseases have an impact on their own cortisol production after prolonged use of systemic steroids. That is, the baseline level of plasma cortisol is <500 nmol, and a correlation with lifelong use of systemic steroids can be demonstrated.

Secondary outcomes:***Cross-sectional study:***

- 1: After a stimulation test, plasma cortisol is not above 500 nmol.
- 2: The increase in plasma cortisol is associated with the intake of systemic steroids.
- 3: Demonstration of the correlation between lifelong use of systemic steroids and the degree of osteopenia and osteoporosis (T-score). T-score from DEXA scanning is used to measure bone density and structure. An affected T-score is defined as follows: T-score between -1.0 and -2.5 = osteopenia and score \leq -2.5 = osteoporosis.
- 4: The number of patients with osteoporosis/penia of the spine and femur is increased compared to expected findings in age-matched individuals.

Exploratory follow-up at 4 months (pilot project):

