- 5: Patients with CRSwNP/CRSsNP/CRS with and without asthma who have shown low adherence <80% after the cross-sectional study and who have achieved adherence over 80% at follow-up have also developed adrenal function impairment with a reduction in plasma cortisol of at least 8% (exploratory study).

Study design (brief description):

The study design is a cross-sectional study of newly referred patients to the Luftvejsklinik, ENT, RH for investigation and treatment of CRS and possibly asthma. And an exploratory follow-up (pilot project) study of patients who attend 4-month control.

Background:

Chronic rhinosinusitis (CRS) is a condition with chronic inflammation in the nose and sinuses. CRS can be with both nasal polyps (CRSwNP) and without polyps (CRSsNP) (5). 9% of the Danish population is affected by CRS, and about 4% are estimated to be diagnosed with CRSwNP (1). The diagnosis is based on the patient's symptoms and objective signs of inflammation in the nose and sinuses. The symptoms are a blocked nose or nasal secretion, reduced airflow, reduced sense of smell, pain/pressure around the nose, forehead, or eyes. The above symptoms must have been present for more than 12 weeks, and one of the symptoms must be secretion or reduced airflow through the nose to make a diagnosis (6). About 40% of CRS patients in primary care have asthma, whereas 65% referred for treatment at the hospital have asthma (7). CRSwNP that is not satisfactorily controlled particularly affects quality of life (8). It is often characterized by type-2 inflammation, i.e., an increased number of eosinophils in the mucous membranes in the sinuses and nasal polyps - as well as comorbidities such as asthma, ASA/NSAID intolerance (N-ERD), and allergies (5). CRS can be treated both surgically and medically. The basic medical treatment of CRS includes daily saline irrigation and use of nasal steroids. If there is a lot of secretion, antibiotic treatment can also be added to the basic treatment. In the case of nasal polyps, systemic corticosteroid treatment (prednisolone tablets/injection betamethasone) can also be added (5,6). If the medical treatment is not

optimal, patients can be offered surgical treatment - endoscopic sinus surgery (ESS) (5). The goal is to aim for the removal of polyps in the nose and sinuses.

Comorbidity:

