The term adherence describes the patient's adherence to the treatment strategy developed in consultation with a healthcare provider. The patient is considered an active participant in their treatment. Adherence can be measured both for pharmacological and non-pharmacological treatment. The WHO categorizes adherence measurements into subjective and objective measurements (11,12). Objective measurements include measurements such as pill counting, electronic monitoring (shared medical record), or biochemical measurements (e.g., blood tests) (11). Subjective measurements require an assessment by a healthcare professional or the patient themselves. Self-reporting by the patient or assessment by the healthcare provider is the most common method used to assess patient adherence. Foster's score and MARS-5 are subjective tools for measuring patient adherence. With Foster's score, the patient is asked a single question, "How many days out of seven do you take your medicine as recommended?" Starting at 0, the score is calculated as the number of days of taking the prescribed amount. Zero days are equal to 0% assessed adherence and taking the medication every day for seven days is equal to 100% assessed adherence (13). MARS-5 - developed by [name] (14,15). MARS-5 is a generic tool. It has been validated in many different clinical settings, including patients with asthma (16).

Poor adherence is especially seen with prolonged treatments among chronically ill patients, underscoring the importance of focusing on sustained adherence in these patients (17). Some patients discontinue their treatment once they have symptom control, after which an exacerbation occurs. They resume their treatment with the feeling that "it does not help" because they experience worsening symptoms (18). WHO estimates that only 50% of patients receiving long-term pharmacological treatment for their chronic illnesses are adherent to their treatment (18,19). Adherence to asthma and COPD has been found to range from 22% to 78% (10,18). In connection with "usual care," patients with asthma receive information, education, and training in relation to their disease in many places. Adherence to pharmacological treatment depends on age, educational level, knowledge of asthma, how many times medication is to be taken, whether the medication is easy to take, and how their communication is with the healthcare

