In the exploratory follow-up at 4 months (pilot project), we will investigate whether good adherence (>80%) to nasal steroids versus continued poor adherence (<80%) changes in P-cortisol compared to measurement of P-cortisol from the cross-sectional study. It is not known whether good adherence (>80%) changes adrenal function. This pilot project will be used for a possible future study, where the effect of adherence will be the primary focus. Therefore, we will include all 80 patients from the cross-sectional study and divide their results into good and poor adherence.

Extraction of biological material:

A maximum of 14 ml of blood is extracted during each Synacthen test (minimum 0.5-3.5 ml maximum split tube x 2-, and 3.5-ml maximum x 2 for the first blood sample for P-cortisol baseline and for the second blood sample for P-cortisol determination). The first blood sample is collected for P-cortisol measurement before the IV injection of ACTH and a minimum of 0.5 ml and a maximum of 3.5 ml of blood is extracted. The second blood sample is collected after 30 minutes following the IV injection of ACTH, and a minimum of 0.5 ml and a maximum of 3.5 ml of blood is extracted. The material is destroyed after analysis. Therefore, no research biobank will be established.

Information from patient records:

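### The pilot asks what improved adherence does to cortisol, but splits all 80 patients at 80%, so patients who were already adherent count as good without any improvement

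*Protocol*

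**What the plan says.** The Purpose section of the Protocol sets the pilot question: "whether improved adherence to local steroid treatment and biologic medication would decrease" the patient's own cortisol production. Secondary outcome 5 makes this operational. It takes patients who were below 80% at the cross-sectional visit and "who have achieved adherence over 80% at follow-up have also developed adrenal function impairment", defined as a fall in plasma cortisol of at least 8%. The pilot's inclusion criteria accordingly require low adherence at the first visit, and its exclusion criteria remove patients above 80%.

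The last paragraph of the power calculation section describes the comparison differently. It contrasts good adherence to nasal steroids (above 80%) with continued poor adherence (below 80%), and then states that "we will include all 80 patients from the cross-sectional study and divide their results into good and poor adherence".

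The Adherence section defines the Foster score as days out of seven: "the score is calculated as the number of days of taking the prescribed amount", and "taking the medication every day for seven days is equal to 100% assessed adherence". The Statistical analysis section names paired tests, Mann-Whitney and chi-square. It names no analysis that uses adherence on its full scale.

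**The concern.** The question is about a change in exposure between two visits. The comparison in the power section sorts patients into two classes, and since all 80 are to be divided, the class cannot depend on having started low. Two things follow.

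- A patient taking treatment seven days out of seven at both visits is classed as good. Exposure has not changed, so on the pilot's own reasoning no cortisol change is expected. Such patients dilute the good group.
- Within the classes the amount of improvement is ignored. A small step across the cut counts fully, and a large gain that stops short of it counts as none.

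The pilot's declared use is to inform a later study with adherence as its primary focus. A diluted estimate, or a null result produced by the grouping, would misdirect that decision.

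**Working it through.** **The plan's own number.** The pilot has no sample-size or power figure. The 72 evaluable patients, and 72 / 0.90 = 80 with dropout, belong to the cross-sectional comparison of 25% with 8% and are unaffected. The simulations below use 72 patients.

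**Population: the statements side by side.**

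| Place in the Protocol | Who is compared |
|---|---|
| Secondary outcome 5 | below 80% first, above 80% at follow-up |
| Pilot inclusion and exclusion criteria | low adherence at first visit; above 80% excluded |
| Power section, pilot paragraph | all 80, divided into good and poor |

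The third row does not fit the first two. The mismatch needs no calculation.

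**Foster arithmetic** (score = days / 7). The eight possible values are 0, 14.3, 28.6, 42.9, 57.1, 71.4, 85.7 and 100%, so the 80% cut falls between 5 and 6 days.

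- 5 to 6 days: 85.7 - 71.4 = 14.3 points gained, classed as good.
- 0 to 5 days: 71.4 - 0 = 71.4 points gained, classed as continued poor.

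These examples hold where the seven-day Foster score decides the group. The pilot criteria also use MARS-5, joined by and/or, and the power section names no instrument for follow-up.

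**Information kept by the split.** The Protocol gives no adherence distribution, so 42 scenarios were assumed: 3 first-visit distributions x 7 follow-up patterns x (low adherers only, or all patients). Information kept is the squared correlation between the split and the adherence measure taken to drive cortisol.

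| What drives cortisol change | Information kept |
|---|---|
| Change in days, low adherers only, unadjusted | 7-42% |
| Change in days, all patients, unadjusted | 0-34% |
| Change in days, adjusted for first-visit adherence | 18-66% |
| Follow-up level | 47-80% |

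In the first row at least 58% is lost; at best 72 x 0.42 = about 30 patients' worth of information remains. With all patients split, 17-59% of the good group had made no gain.

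**Power under three assumed truths.** Assumptions: 72 patients; first-visit Foster days with mean 4.5 and SD 2 (all patients), or mean 3.0 and SD 1.6 capped at 5 (low-only sample); change with mean +1.3 and SD 2.0; residual SD of log cortisol change 0.30. The comparison is a t-test of 6 or more days against fewer, versus regression on change in days alone.

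| Truth | Sample | Split | Regression on change |
|---|---|---|---|
| -0.5 x (change in days / 7) | all | 24% | 88% |
| same | low adherers within that sample | 40% | 79% |
| same | low-only | 48% | 92% |
| Linear in follow-up level | all | 89% | 45% |
| same | low-only | 87% | 84% |
| Fall of 0.25 log in low starters who reach 80% | all | 37% | 47% |
| same | low-only | 88% | 42% |

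Repeat runs differ by a few points. With no effect, all methods reject in 4-6% of runs. About half of the good group in the all-patients version was already good at the first visit. Under the first truth, dropping patients who started above 80% raises the power of the split from 24% to 40%, although fewer patients remain.

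Reporting error of SD 1.2 days per visit lowers the first three rows to 17% against 53%, 21% against 43% and 34% against 63%.

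**Adding first-visit adherence to the regression.** Across six scenarios (effect linear in change or in level) without reporting error, power was 75-93%, against 23-90% for the split. The split was ahead in one scenario, 90% to 82%.

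**The case against.** The strongest reply is that crossing 80% is the protocol's own operational question. The hypothesis speaks of patients who improve to above 80%, secondary outcome 5 is a crossing of 80%, and the Method section measures cortisol in patients who have reached it. For patients who start low, the good-versus-poor comparison answers that question, and a slope per day answers a different one. This stands. It is why the split should be kept for low starters, and it gives no support to dividing all 80.

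A reader might infer from the Foster examples that most of the information is lost whatever the truth, and that regression on change should replace the split. The documents do not support this. The large losses assume that cortisol responds in proportion to the change in days. If the effect is a step at 80%, the split has 88% power in low adherers and regression on change 42%. If follow-up level is what matters, the split loses 20-53% of the information and beats regression on change in the all-patients sample.

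It is also fair that this is an exploratory pilot with no power claim, that the graded scores are collected, and that a statistical analysis plan not shown here may add modelling. That limits the weight. It does not remove the point, because the Protocol itself fixes the population and the cut, and the population contradicts its own criteria.

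**Conclusion.** The concern holds in two parts of different strength.

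The firm part rests on the text alone. Dividing all 80 patients at 80% puts patients who were already adherent into the good group without any improvement. This departs from the stated purpose and secondary outcome 5, and conflicts with the pilot's inclusion and exclusion criteria.

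The second part is conditional. The split discards a substantial part of the adherence information, and more than half if the amount of improvement drives cortisol and the comparison is not adjusted for first-visit adherence. With that adjustment the loss is 34-82%; if follow-up level drives cortisol it is 20-53%. All these figures rest on assumed adherence distributions, and the power figures also on an assumed effect and SD. A flat statement that most of the information is lost would go beyond the documents. The information is lost in the analysis and not in the data, so it can be recovered.

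**What to change.** In the pilot paragraph of the power calculation section:

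1. Restrict the good-versus-continued-poor comparison to patients with adherence below 80% at the first visit, in line with secondary outcome 5. Reconcile this with the sentence on all 80 patients and with the pilot's criteria, and name the instrument that decides the group at follow-up.
2. Add a linear model in all patients: four-month P-cortisol on change in adherence (Foster days per week, four months minus first visit), with first-visit P-cortisol and first-visit adherence as covariates. First-visit adherence is needed because the possible gain is limited by the starting score. Report the slope with its 95% CI, and repeat with MARS-5.
3. Report both analyses.

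The cost is wording only. The Method section already plans the Synacthen test at both visits for all patients, and the questionnaires are routine in the clinic. The downside is that the graded model assumes a roughly linear relation, which a plot can check, and that it is less powerful than the split if the effect is a step at 80%. That is the reason to report both.
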